8.0 Study Endpoints*

8.1 Primary Endpoint:

The primary endpoint is feasibility and acceptability as measured by participant rates of enrollment (>50%), participant retention (>70%), intervention attendance (>70% attending at least 4 of 6 sessions), and intervention satisfaction (>75% reporting average satisfaction greater than the scale's midpoint).

8.2 Secondary Endpoints:

The secondary endpoints of the study are as follows:

- Changes in adherence between groups on objective MEMS Caps and self-report MARS-5* at 12-weeks and 24-weeks post-baseline (changes in MEMS Caps adherence will be compared across the entire 24-week period).
- Changes in self-reported satisfaction with AET on the CTSQ* between groups at 12-week and 24-weeks post-baseline.
- Changes in self-reported symptom distress on the BCPT* between groups at 12-week and 24-weeks post-baseline.

Secondary endpoints will also be examined using social support (MSPSS*) and demographic and treatment-related factors (e.g., age, stage, time since AET initiation) as potential covariates.

8.3 Exploratory Endpoints:

- Changes in distress levels (HADS*), quality of life (FACT-B*), and medication self-efficacy (SEAMS*) between groups at 10- and 24-weeks post-baseline, as well as potential mediation of secondary and exploratory endpoints through changes in beliefs about adjuvant endocrine therapy (BMQ-AET*), self-efficacy for managing AET symptoms (Self-Efficacy For Symptoms) and/or perceived coping skills (MOCS*). Potential demographic or treatment related moderators will also be explored (e.g., age, type of AET medication, cognitive functioning [PROMIS*]).

*All study instruments are explained in full in Section 9.3.

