This will be the first study to develop and test an evidence-based intervention that is flexible, portable, and tailored to address AET adherence barriers unique to BCS. The proposed strategy implements a mixed-methods design based on the ORBIT model,¹ integrates a comprehensive conceptual framework, adapts an established, evidence-based treatment, and employs novel technologies in the following three ways: 1) Tailored intervention content. 2) Videoconferencing. The use of tele-mental health ZOOM technology limits barriers to treatment such as cost, time, and travel, thereby increasing access to behavioral health interventions.⁸ We will extend the use of videoconferencing to BCS reporting difficulty managing their AET. 3) Objective, electronic measurement. Since self-report methods tend to yield overestimates of adherence,⁹⁻¹² We will use the Medication Event Monitoring System (MEMS¹³) in addition to self-report measures. Thus, this study employs existing technologies in a novel setting to model longitudinal change in AET adherence in the intervention and control groups.¹³

Specific Aims

1. **Primary Aim.** To examine the feasibility and acceptability of a tailored, small-group, Telehealth intervention (STRIDE) compared to a medication monitoring control for survivors of breast cancer taking AET.

Hypothesis 1: The study will be feasible, defined by recruitment (enrollment rate > 50%), retention (follow-up assessment completion rate > 70% of all participants who complete baseline) and attendance (attendance rate of at least 70% of participants completing at least 4 of 6 sessions [67%]).

Hypothesis 2: The study will be acceptable demonstrated by >75% of participants reporting average satisfaction scores greater than the scale's mid-point (Client Satisfaction Questionnaire).

2. **Secondary Aim:** To assess effects of the STRIDE intervention on adherence to AET, symptom distress, and satisfaction with AET.

Hypothesis 2: We hypothesize that participation in the STRIDE intervention will be associated with an increase in adherence and satisfaction with AET and a decrease in symptom distress at 12-weeks compared to the medication monitoring control, and that these improvements will maintain at 24-week follow-up.

3. **Exploratory Aims:**

- a. To assess the effects of the STRIDE intervention on several psychosocial constructs, exploring potential mediator and moderators of the intervention.

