10.0 Data and Specimen Banking: Not applicable

11.0 Data Management* and Confidentiality

11.1 Data Analysis

To determine feasibility in a pilot randomized controlled trial (N=100), estimate effect size, and finalize the intervention and study protocol to plan a full-scale, adequately powered efficacy trial.

Power calculation. The primary objective of this pilot study is to demonstrate feasibility, defined as (1) enrollment rate > 50%, (2) retention rate > 70%, and (3) attendance rate \geq 70% (i.e. \geq 70% of participants complete at least 4 of 6 sessions). At the time of the original protocol approval, we

estimated an accrual goal of 80 (75 in RCT and 5 in run-in phase) participants; therefore, the following power estimates are based on that number. We estimated that the enrollment rate will be 60%. If 134 patients are approached and 80 are enrolled, the lower limit for an exact, one-sided 95% confidence interval for the estimated enrollment rate will be 53%. Furthermore, we anticipate that the retention and attendance rates will both be 80%, and with 80 enrolled participants, the lower limit for an exact, one-sided 95% confidence interval for the retention and attendance rates will be 71%. Thus, based on our estimates of the feasibility parameters, the study will demonstrate feasibility of the adherence intervention. We have now expanded our accrual goal to 100 participants, which serves to only increase our power and rates of enrollment, retention, and attendance.

Primary Aim. To examine the feasibility and acceptability of a tailored, small-group, Telehealth intervention (STRIDE) compared to a medication monitoring control for survivors of breast cancer taking adjuvant endocrine therapy.

Hypothesis 1: The study will be feasible, defined by recruitment (enrollment rate > 50%), retention (completion rate of follow-up assessments > 70% of all participants who complete baseline) and attendance (attendance rate of at least 70% of participants completing at least 4 of 6 sessions [60%]).

Hypothesis 2: The study will be acceptable demonstrated by >75% of participants reporting average satisfaction scores greater than the scale's mid-point (Client Satisfaction Questionnaire).

Secondary Aim. To assess effects of the STRIDE intervention on adherence to AET, symptom distress, and satisfaction with AET.

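### Section 11.1 supports the feasibility claim with exact lower confidence limits that the written feasibility rule does not use, and the attendance limit rests on the wrong denominator

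*Combined protocol and SAP*

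**What the plan says.** Three places define feasibility, all by observed rates without an interval. Section 8.1 gives "measured by participant rates of enrollment (>50%), participant retention (>70%), intervention attendance (>70% attending at least 4 of 6 sessions"). Hypothesis 1 in the Specific Aims reads "The study will be feasible, defined by recruitment (enrollment rate > 50%), retention (follow-up assessment completion rate > 70% of all participants who complete baseline"). The opening of the Power calculation in 11.1, and Hypothesis 1 as repeated there, do the same.

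The attendance threshold is not the same throughout. Section 8.1 is strict: "intervention attendance (>70% attending at least 4 of 6 sessions"). The Specific Aims are not: "attendance rate of at least 70% of participants completing at least 4 of 6 sessions [67"%]. Section 11.1 also uses the non-strict form.

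The Power calculation then turns to confidence limits. It assumes 80 of 134 approached women enroll and gives a lower limit of 53%. For retention and attendance it plans on 80% each, counted over all 80 women enrolled, and reports that "the lower limit for an exact, one-sided 95% confidence interval for the retention and attendance rates will be 71"%. It concludes: "Thus, based on our estimates of the feasibility parameters, the study will demonstrate feasibility of the adherence intervention". It adds that the later expansion to 100 can only help, but does not recompute the limits.

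Section 9.2 says that control participants do not receive STRIDE.

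**The concern.** The conclusion in 11.1 follows from the lower limits only if clearing the limit is what shows feasibility. Under the written definition the limits play no part: 71 of 100 retained meets the criterion, although its exact lower limit is 62.6%. A reader of 11.1 would credit the feasibility claim with the error control of a one-sided 95% limit, which the rule does not have.

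Feasibility is part of the primary endpoint, and 7.0 and 11.1 say that the findings will feed a grant proposal for a full-scale trial. The strength of the claim should therefore be stated correctly.

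**Working it through.** **Inputs.** Thresholds of 50%, 70% and 70% (8.1); planned rates of 60%, 80% and 80% (11.1); RCT size 100 plus 5 run-in (4.0).

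Assumed:
- 175 approached, from 105 / 0.60.
- 100 women in the retention denominator.
- 50 STRIDE women. No allocation ratio is stated, but the lists in Appendix 30.8 hold the two arms in near-equal numbers.
- Independent criteria, for the joint figures.

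**Formulas.** The exact one-sided 95% lower limit for x of n is the 5th percentile of Beta(x, n − x + 1). The chance of meeting a criterion is the binomial tail P(X ≥ r), with r the smallest passing count.

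**The plan's own figures.** 64/80 gives 71.2%, which reproduces the stated 71%. 80/134 gives 52.2% against the stated 53%; a normal approximation at 60% gives 53.0%. The enrollment figure is thus close, but not quite the exact limit it is said to be.

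**Attendance with the intervention arm as denominator.** At the planned 80%, 40/50 has a lower limit of 68.4%, below 70%. The limit first clears 70% at 41/50 (70.7%). For comparison, 80/100 retained gives 72.3% and 105/175 enrolled gives 53.5%, so those two still clear at the planned rates.

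**Chance of meeting each criterion**

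| Criterion | Written rule needs | True rate at cut-off | At planned rate | Limit would need | True rate at cut-off | At planned rate |
|---|---|---|---|---|---|---|
| Enrollment | 88/175 | 50.0% | 99.6% | 99/175 | 4.8% | 84.2% |
| Retention | 71/100 | 46.2% | 98.9% | 78/100 | 4.8% | 73.9% |
| Attendance, >70% | 36/50 | 44.7% | 93.9% | 41/50 | 4.0% | 44.4% |
| Attendance, ≥70% | 35/50 | 56.9% | 96.9% | 41/50 | 4.0% | 44.4% |

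**Sensitivity to arm size.** For 45 to 55 STRIDE women with true attendance of 70%, the chance is 44.7% to 55.9% (strict) or 46.0% to 56.9% (non-strict).

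**All three feasibility criteria together** (satisfaction not included). With attendance truly 70% and the other two as planned:
- strict: 0.447 × 0.989 × 0.996 = 44%
- non-strict: 0.569 × 0.989 × 0.996 = 56%

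Requiring all three adds almost no protection when two rates are comfortably above their cut-offs.

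**If the limits were decisive**, the planned rates would meet all three with chance 0.842 × 0.739 × 0.444 = 27.6%.

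**The case against.** The strongest reply is that there is only one rule. Every definition of feasibility, including the one that opens the Power calculation, is an observed rate. On this view the intervals only show precision at the anticipated values, and observed benchmarks are a reasonable choice for a pilot that 11.1 says is not powered for group differences. Most of this stands. A reader might infer that 11.1 sets a second decision rule under which the limits must clear the thresholds. The text writes no such rule. What remains is that 11.1 draws its conclusion from the limits, and that this conclusion is not a property of the rule in use.

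A reader might also infer that a study with attendance truly at 70% would be declared feasible more than half the time. The documents do not support that. Under the strict wording of 8.1 with 50 women the figure is 44.7%; it exceeds half at that size only under the non-strict wording, and at nearby arm sizes it falls on either side. Attendance is also only one of several criteria.

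Finally, making the limits decisive would be expensive: an intervention arm performing exactly to plan (40/50) would miss. That is a fair reason not to impose the stricter rule. It is not a reason to keep a justification that relies on it.

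**Conclusion.** The point holds as a mismatch between the justification and the rule. The lower limits in 11.1 do not support its concluding claim, because the written criteria do not use them: at the cut-off those criteria are met 45% to 57% of the time, against 4% to 5% under the limits. For attendance the assurance also fails on its own terms once the denominator is the intervention arm.

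The exact percentages rest on the assumed 175 approached, 100 in the retention denominator and 50 STRIDE women; the joint figures also need independence. Moderate changes in these would not remove a contrast of this size. The conflict between the strict and non-strict attendance thresholds needs no assumption. Using observed thresholds in a pilot is not itself an error.

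**What to change.** 1. In 8.1 and both statements of Hypothesis 1, keep the thresholds as observed benchmarks (target met or not met), and report the exact one-sided 95% lower limit beside each rate.
2. In 11.1, recompute the limits for the current sizes, with the intervention arm as the attendance denominator.
3. Delete the concluding claim of the Power calculation, or limit it to criteria whose lower limit clears the threshold.
4. State the chance that the rule actually used is met, at the cut-offs and at the planned rates.
5. Choose one attendance threshold, strict or non-strict, and use it throughout.

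This needs wording changes and one interval per criterion, with no new data or participants. The cost is that the assurance in 11.1 becomes less favourable, above all for attendance. Making the limits decisive is a further option for the sponsor; if it is taken, the 28% joint chance at the planned rates should be stated with it.

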9.0 Procedures Involved*

9.1 Study Design

This is a multi-site randomized control trial of a tailored, telehealth intervention (STRIDE) versus standard care plus medication monitoring in up to 105 BCS taking AET (run-in period, n=5; RCT, n=100). To ensure balanced representation between the two study groups, we will stratify randomization by participant level of distress (high vs. low), determined by HADS administered at baseline (Appendix 30.8). A participant will be considered high distress if they answer with a score of ≥ 8 on the HADS. Furthermore, participants who self-identify as part of a minority identifying racial/ethnic group will be offered the opportunity to participate in a qualitative exit interview to gather patient feedback on the study's cultural awareness and relevance. This interview will take approximately 15 minutes.

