Psychiatric symptoms are highly prevalent in BCS prescribed AET. Of the 240 women who participated in the CBSM study, 67% were prescribed AET. One-year post-surgery, 27.6% of these women reported elevated depressive symptoms, and 37.0% reported elevated anxiety. These findings are comparable to population rates, highlighting the need to mitigate distress in BCS taking AET. Furthermore, preliminary data from our ongoing studies in the Cancer Outcomes Research Program, co-directed by [name] and [name], suggest that the proportion of MGH patients with breast cancer and depression and/or anxiety is congruent with published estimates of up to 33% of BCS reporting anxiety or depressive symptoms.^{73,74} Specifically, in a current Patient-Centered Outcomes Research Institute-funded study (PI: [name]) to improve adherence and symptom management in patients with cancer prescribed oral chemotherapy, 27% of women with breast cancer at MGH reported clinically elevated levels of anxiety, and 12% reported clinically elevated levels of depression on the Hospital Anxiety and Depression Scale. After completion of active treatment, these women will become eligible for participation in the proposed study. Furthermore, in a survivorship needs assessment survey completed by 130 MGH BCS (PI: [name] and [name]), 46% of women reported experiencing anxiety symptoms “sometimes,” and 22% reported experiencing anxiety symptoms “most of the time” or “always”. In addition, 35% of MGH BCS reported experiencing sadness “sometimes,” and 9% experienced sadness “most of the time” or “always.” Of these MGH BCS who were prescribed AET, 57% reported experiencing anxiety symptoms “sometimes,” 22% reported experiencing anxiety symptoms “most of the time” or “always,” 51% reported experiencing depressive symptoms “sometimes”, and 5% reported depressive symptoms “most of the time” or “always.”

Systematic review finds few interventions for AET adherence. I collaborated with [name] to publish a systematic review of adherence to oral cancer therapy,¹² which identified three of the RCTs with interventions to improve adherence to AET in early-stage breast cancer. Interventions were atheoretical and not efficacious.^{10,26,27} Conclusions underscore the need for theoretically- and evidence-based interventions targeting AET adherence in BCS.

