Hospital Anxiety and Depression Scale (HADS):⁶¹ The HADS is a valid self-report measure for assessing anxiety and depressive symptoms among patients in non-psychiatric hospitals.⁶² The 14-item measure contains seven questions to assess depressive symptoms and seven questions to assess anxiety symptoms to distinguish between the two. Patients indicate how they have been feeling on average over the past week. Each item is answered on a scale of 1 to 4. The four possible answer choices vary and adjust for each question.

Functional Assessment of Cancer Therapy-Breast Cancer (FACT-B): The FACT-B is a validated measure used to assess multidimensional quality of life in patients with breast cancer. The measure captures five domains: physical well-being, social/family well-being, emotional well-being, functional

well-being, and additional concerns. Each item is answered on a scale of 0 (not at all) to 5 (very much).⁶³

Self-Efficacy for Appropriate Medication Use Scale (SEAMS):⁶⁴ The SEAMS will be used to measure patient self-efficacy in taking medication. The SEAMS was developed specifically for patients with chronic disease taking long-term medication.⁶⁴ Two factor structures are created: self-efficacy for taking medication under difficult circumstances and under changing circumstances. Each item is answered on a scale of 1 (not confident) to 3 (very confident).

Covariates:

EHR Factors: The following information will be collected from participant EHR: MGH Main vs. Affiliate site, health insurance type, breast cancer stage, treatment (e.g., surgery, chemotherapy, radiation), ET type, time since treatment completion, menopausal status, psychotropic medications, and medical or psychological co-morbidities.

Demographic Questionnaire: Participants will self-report their age, gender, race/ethnicity, marital status, education level, and relationship status.

Multidimensional Scale of Perceived Social Support (MSPSS):⁶⁵ The MSPSS is a validated, reliable scale used to capture levels of perceived social support. The scale consists of 12 items, such as “my family really tries to help me,” and is measured on a 7-point Likert scale.

Potential Mediators

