20.2 Site Resources

On an average year, 517 women with newly diagnosed breast cancer were treated with AET at the MGH Cancer Center. Based on literature and our initial findings from Phase 1 of this study, we expect up to 40% will have poor adherence and between 20-25% will have distress. Patients will screen in if they are experiencing distress related to AET, adherence, or side effects, they would be eligible for the study; therefore, we estimate the number of eligible patients may range from 104-208 patients per year.

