For registration of patients from DF/HCC institutions, which will be all participants in this study, study staff will complete the DF/HCC protocol-specific eligibility checklist using the eligibility assessment

documented in the participant's EHR and/or research chart. Study staff will confirm that the participant meets all inclusion criteria as described in this protocol and the criteria on the eligibility checklist. Study staff will be responsible for self-randomization of participants (Biostatistician-generated Randomization Scheme: Appendix 30.8) per ODQ request to decentralize non-therapeutic studies under the DF/HCC. MGH study staff will follow DF/HCC Standard Operating Procedure for Human Subject Research Titled *Subject Protocol Registration* (SOP #: REGIST-101) and register the participant on the protocol.

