19. How satisfied were you with the **form** of your hormonal therapy (pills)?

5 4 3 2 1
Very satisfied Satisfied Neither satisfied nor dissatisfied Dissatisfied Very dissatisfied

20. Overall, how satisfied were you with your most recent hormonal therapy (pills)?

5 4 3 2 1
Very satisfied Satisfied Neither satisfied nor dissatisfied Dissatisfied Very dissatisfied

21. Taking everything into consideration, if given the choice again, would you decide to take this hormonal therapy?

5 4 3 2 1
Yes, definitely Probably Yes I don't know Probably not Definitely not

Hospital Anxiety and Depression Scale

HADS

INSTRUCTIONS: Read each item and please select the answer which comes closest to how you have been feeling, on the average, IN THE PAST WEEK.

01. I feel tense or "wound up."

1. Most of the time
2. A lot of the time
3. From time to time, occasionally
4. Not at all

02. I still enjoy the things I used to enjoy.

1. Definitely as much
2. Not quite as much
3. Only a little
4. Hardly at all

03. I get a sort of frightened feeling as if something awful is about to happen.

1. Very definitely and quite badly
2. Yes, but not too badly
3. A little, but it doesn't worry me
4. Not at all

04. I can laugh and see the funny side of things.

1. As much as I always could
2. Not quite so much now
3. Definitely not so much now
4. Not at all

05. Worrying thoughts go through my mind.

1. A great deal of the time
2. A lot of the time
3. From time to time but not too often
4. Only occasionally

06. I feel cheerful.

1. Not at all
2. Not often
3. Sometimes
4. Most of the time

07. I can sit at ease and feel relaxed.

1. Definitely
2. Usually
3. Not often
4. Not at all

08. I feel as if I am slowed down.

1. Nearly all the time

2. Very often
3. Sometimes
4. Not at all

09. I get a sort of frightened feeling like "butterflies" in the stomach.

1. Not at all
2. Occasionally
3. Quite often
4. Very often

10. I have lost interest in my appearance.

1. Definitely
2. I don't take so much care as I should
3. I may not take quite as much care
4. I take just as much care as ever

11. I feel restless as if I have to be on the move.

1. Very much indeed
2. Quite a lot
3. Not very much
4. Not at all

12. I look forward with enjoyment to things.

1. As much as I ever did
2. Rather less than I used to
3. Definitely less than I used to
4. Hardly at all

13. I get sudden feelings of panic.

1. Very often indeed
2. Quite often
3. Not very often
4. Not at all

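### The HADS cut that defines the only stratification factor has no stated score or workable coding, and the analysis models do not name the stratum

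*Combined protocol and SAP*

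**What the plan says.** Section 9.1 stratifies randomisation by distress, high or low, from the baseline HADS. The rule reads "A participant will be considered high distress if they answer with a score of" 8 or more on the HADS, and points to Appendix 30.8. That appendix labels its two lists elevated and not elevated and gives no score.

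Section 9.3, where section 8 says the instruments are explained, describes 14 items in two seven-item subscales, anxiety and depression. On coding it says only "Each item is answered on a scale of 1 to 4". The form in Appendix 30.17 numbers the options 1 to 4, but the direction varies. For "06. I feel cheerful" option 1 is the worst answer; for "07. I can sit at ease and feel relaxed" option 1 is the best. No section gives a reversal or recoding rule.

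Section 14.3 uses a different HADS cut for a different purpose and does name its items (the even ones). Section 27.0 states "Study staff will be responsible for self-randomization of participants", from a scheme generated by the biostatistician.

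For the analysis, 8.2 and 11.1 name social support, age, stage and time since starting endocrine therapy as possible covariates. Section 11.1 plans mixed models over all time points, a cross-sectional analysis at each time point, and Cohen's d on change scores. The distress stratum is not named, though the lists are worded as examples.

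**The concern.** Staff pick the randomisation list from a score that the protocol does not define. Two careful people could place the same woman in different strata, and a later reader could not reproduce the placement. If the rule were applied exactly as written, stratification would do nothing.

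The second gap is in the models. Stratified randomisation removes between-stratum variation from the arm contrast. A model that leaves the stratum out still counts that variation as error, so its standard errors come out too large.

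At stake are the secondary and exploratory arm comparisons, which 11.1 intends to use in sizing a full efficacy trial. HADS is also an exploratory outcome in 8.3, so the missing scoring rule affects an endpoint as well as the stratum.

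**Working it through.** The plan gives no figure of its own on this point to reproduce.

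**1. The cut under the stated coding.** Inputs: 14 items, two subscales of 7, answers 1 to 4 (9.3 and Appendix 30.17).
- Lowest total: 14 × 1 = 14. Every participant is at 8 or more.
- Lowest subscale: 7 × 1 = 7. There are 4^7 = 16,384 answer patterns, and exactly one scores below 8.

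**2. Direction of the printed options.** Option 1 is worst on items 1, 3, 5, 6, 8, 10, 11 and 13, and best on 2, 4, 7, 9, 12 and 14. Summing the printed numbers without reversal gives:

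| Score | Symptom-free | Worst |
|---|---|---|
| Odd items (anxiety) | 5×4 + 2×1 = 22 | 5×1 + 2×4 = 13 |
| Even items (depression) | 3×4 + 4×1 = 16 | 3×1 + 4×4 = 19 |
| Total | 38 | 32 |

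The total and the anxiety score run backwards, so a scoring step is needed and none is written.

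**3. Total against subscale under a workable coding.** Assume items aligned in direction and recoded 0 to 3, which the documents do not state. A woman low on both subscales has each at 0 to 7, giving 8 × 8 = 64 score pairs. The pairs summing to 8 or more number 1 + 2 + … + 7 = 28. For example, anxiety 4 and depression 4 is low on both subscales and high on the total. These are score combinations, not a share of women.

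**4. Omitting the stratum, cross-sectional comparison.** If the arms are balanced within strata that explain a share R² of the outcome level, the reported standard error exceeds the true one by 1/√(1 − R²) − 1. R² is an assumption; the documents give none.

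| R² | Excess |
|---|---|
| 0.01 | 0.5% |
| 0.05 | 2.6% |
| 0.10 | 5.4% |
| 0.20 | 11.8% |

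In a simulation (100 women, two equal strata, 1:1 within stratum, one time point, 20,000 runs, two-sided 0.05), the type I error without the stratum was 0.039 at R² = 0.10 and 0.028 at 0.20. With the stratum it was 0.050 and 0.049.

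**5. Omitting the stratum, change contrasts.** A stratum effect that is constant over visits cancels when baseline is subtracted. In a simulated random-intercept model with complete data (100 women, three visits, stratum effect of one SD of the person intercept), the arm-by-time estimate was 0.0115 with standard error 0.1935, both with and without the stratum main effect. Only the part of the stratum effect that predicts change matters, and it needs a stratum-by-time term.

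**The case against.** The strongest reply is that nobody would score the HADS literally. Section 2.0 reports HADS results by subscale from another study at the same centre: "27% of women with breast cancer at MGH reported clinically elevated levels of anxiety, and 12% reported clinically elevated levels of depression". Section 14.3's even-item rule of 11 or more would catch a symptom-free woman, at 16, if printed codes were summed unreversed. Appendix 30.8 provides a list for women who are not elevated. Section 12.1 also promises a study-specific data dictionary, where a scoring rule could sit.

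Most of this stands. A reader might infer from the minimum total of 14 that the low stratum was empty and stratification failed. The documents do not support that, because these sections point to a scoring that separates patients. They do not supply the rule, however. The 2.0 figures come from a different study, 14.3 argues for reversal but not for a particular recoding, the lists were drawn up in advance, and 12.1 does not mention HADS scoring. None settles total against subscale.

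A reader might also infer that leaving the stratum out biases the comparisons or widens every standard error. Neither follows. Randomisation is valid under any consistent stratum, so the estimates are unbiased. The widening applies to comparisons of level at one time point. For arm-by-time contrasts and the change-score d it depends on how far the stratum predicts change, for which the documents give no value.

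Finally, 11.1 says that the pilot is not powered for group differences, and the primary endpoint is feasibility and acceptability. That is correct and limits the weight of the point.

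**Conclusion.** The point holds as two gaps in the written plan. First, the stratum cut is not tied to a defined HADS score, and with the only coding stated it cannot separate high from low distress. Whether staff applied a sound unwritten rule cannot be told from the documents. Second, the sole stratification factor is unnamed, though not excluded, in the models. Omitting it costs about 0.5% to 12% in the standard errors of the cross-sectional comparisons. This assumes that the stratification worked and that the stratum explains 1% to 20% of the outcome level. There is no bias. The effect on change contrasts cannot be quantified from the documents, and the feasibility endpoints are untouched. This is a minor-to-moderate point, confined to the secondary and exploratory comparisons.

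**What to change.** - **Sections 9.1 and 9.3:** state the HADS score that defines the stratum: the total or a named subscale, the item codes, and which items are reversed.
- **Check of data held:** rescore the stored baseline item responses and report how many randomised participants were placed in a stratum other than the one the stated score gives.
- **Section 11.1:** include the stratum as randomised as a fixed effect in the cross-sectional comparisons, and as stratum plus stratum-by-time in the longitudinal models. If the check finds mis-scoring, add a sensitivity analysis with correctly scored baseline HADS.
- **Reconciliation:** make the HADS coding consistent across 9.1, 9.3, 14.3 and Appendix 30.17. The follow-up rule in 14.3 rests on the same items and is flagged only for consistency; no clinical threshold is proposed.

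The cost is a few sentences and a rescoring of forms already collected. No new data are needed.
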